10.3 Secondary Efficacy Analyses

10.3.1 CR + CRi Rate

CR + CRi rate will be defined as the proportion of subjects who achieve a complete remission or complete remission with incomplete blood count recovery (CR + CRi) at any time point during the study per the modified IWG criteria for AML. Subjects who are randomized but have no IWG disease assessment will be considered to be non-responders in the calculation of CR + CRi rate. All subjects in the full analysis set will be included in the analysis.

CR + CRi rate will be compared between treatment arms using Cochran-Mantel-Haenszel (CMH) test, stratified by AML status (de novo, secondary) and age (18 – < 75, ≥ 75). In addition, the 95% confidence interval for CR + CRi rate based on the binomial distribution (Clopper-Pearson exact method) by treatment arms will be provided. The risk difference and 95% confidence interval for the risk difference (exact unconditional confidence limits) will also be provided.

10.3.2 CR + CRh Rate

CRh (Complete remission with partial hematologic recovery) is a derived response based on bone marrow blast and hematology lab values. A subject achieves a CRh when meeting the following criteria:

- Bone marrow with < 5% blasts and
- Peripheral blood neutrophil count of $> 0.5 \times 10^3/\mu\text{L}$ and
- Peripheral blood platelet count of $> 0.5 \times 10^5/\mu\text{L}$ and
- A 1 week (≥ 7 days) platelet transfusion-free period prior to the hematology lab collection.

For a bone marrow sample collected before the last cycle of study treatment, the hematology lab results collected from the date of the bone marrow sample collection up to the Day 1 of a subsequent cycle of study treatment will be used for CRh analysis. For a bone marrow sample collected during or after the last cycle of study treatment, the hematology lab results collected within 14 days after bone marrow sample collection date will be used for CRh analysis.

CR + CRh rate will be defined as the proportion of subjects who achieve a complete remission (CR) or complete remission with partial hematologic recovery (CRh) at any time point during the study. Subjects who are randomized but have no disease assessment will be considered as non-responders in the calculation of CR + CRh rate. All subjects in the full analysis set will be included in the analysis.

CR + CRh rate will be compared between treatment arms using Cochran-Mantel-Haenszel (CMH) test stratified by AML status (de novo, secondary) and age ($18 < 75, \geq 75$). In addition, the 95% confidence interval for CR + CRh rate based on the binomial distribution (Clopper-Pearson exact method) by treatment arms will be provided. The risk difference and the 95% confidence interval for the risk difference (exact unconditional confidence limits) will also be provided.

10.3.3 CR + CRh and CR + CRi rate by the Initiation of Cycle 2

CR + CRh rate by the initiation of Cycle 2 will be defined as the proportion of subjects who achieved a complete remission (CR) or complete remission with partial hematologic recovery (CRh) by the initiation of Cycle 2. Subjects who are randomized but have no disease assessments by the initiation of Cycle 2 will be considered to be non-responders in the calculation of CR + CRh rate by the initiation of Cycle 2. For subjects who discontinue the treatment before initiation of Cycle 2, all disease assessments evaluated before the cutoff date and the initiation of post treatment therapy, whichever occurs earlier, will be included. All subjects in the full analysis set will be included in the analysis.

CR + CRh rate by the initiation of Cycle 2 will be compared between treatment arms using Cochran-Mantel-Haenszel (CMH) test stratified by AML status (de novo, secondary) and age ($18 < 75, \geq 75$). In addition, the 95% confidence interval for CR + CRh rate by the initiation of Cycle 2 based on the binomial distribution (Clopper-Pearson exact method) by treatment arms will be provided. The risk difference and the 95% confidence interval for the risk difference (exact unconditional confidence limits) will also be provided.

Similar analyses will be performed for CR + CRi rate by the initiation of Cycle 2.

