5.1.4 Post Treatment Follow-Up

After study treatment has ended and subjects have completed their Final Visit, subjects will be followed for overall survival, progressive disease and post-therapy disease status (if applicable). Survival information and post treatment follow up (i.e., the date and cause of death, all post treatment cancer therapies including transplantation, regimens, dates of initiation and completion, etc.) will be collected (e.g., via telephone calls and/or clinical visits) every 2 months until the end of the study. All subjects will be followed for

survival information (i.e., date and cause of death) unless the subject requests to be withdrawn specifically from this study survival follow-up; this request must be documented in the subject's medical record and signed by the Investigator. In such instances, sites may enter confirmation of death using source documentation from publically available records such as death certificates or funeral notices.

For subjects who had CR, CRi, MLFS, or PR at time of study drug discontinuation, hematology and disease assessments data will also be collected every 2 months (\pm 14 days) for 2 years after the last subject has been enrolled into the study.

For subjects who had RD, MR or PD at time of study drug discontinuation, survival phone calls will be conducted every 2 months (\pm 14 days) for 2 years after the last subject has been enrolled into the study.

30 Day Safety Follow-Up Visit

A Safety Follow-Up Visit should be performed for all subjects approximately 30 days following discontinuation of study drug and then as clinically appropriate for safety assessment. The subject will be followed until a satisfactory clinical resolution of the adverse event is achieved.

A Safety Follow-Up Visit does not need to be performed for subjects who had a Final Visit conducted $>$ 30 days after discontinuation of study drug and did not require additional adverse event follow-up. If the subject refuses or is unable to attend the Safety Follow-Up Visit, this should be noted in the subject's source documentation.

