- End of Cycle 1 (must be performed within ± 3 days of Cycle 1 Day 28 and resulted prior to the administration of treatment for Cycle 2).
- For subjects with resistant disease at end of Cycle 1 a repeat bone marrow must be performed at the end of Cycle 2 or Cycle 3 based on the hematologic recovery to assess for a response of CR/CRi.

- For subjects with a response of CRi on two successive bone marrow samples, an additional bone marrow aspirate and biopsy must be performed to confirm a CR once peripheral blood count recovery is noted. This is not required for subjects who are unblinded following the final analysis results.
- For all subjects a bone marrow aspirate and biopsy must be performed at end of Cycle 4 and every 3 cycles (\pm 1 week) thereafter. This is not required for subjects who are unblinded following the final analysis results. Bone marrow aspirate and/or biopsy can be completed as per institutional standard of care.
- Upon concern for relapse or progressive disease.
- Final Visit (if no BM collected within the last 6 – 8 weeks. Disease assessment is not required if relapse of disease has already been confirmed.)

A bone marrow aspirate and biopsy must be performed for all subjects during screening to confirm diagnosis and to collect mandatory samples for mandatory biomarker assessments. Historical bone marrow aspirates and biopsies assessed locally to confirm the diagnosis may be used as baseline assessment to satisfy eligibility criteria if they were collected as standard of care within 30 days prior to randomization. During screening, after informed consent is signed, bone marrow aspirates and biopsies may be collected to confirm the diagnosis to satisfy eligibility criteria.

During screening, after informed consent is signed, a bone marrow aspirate must be performed for all subjects to collect samples for mandatory biomarker assessments (*biomarker collections are not applicable to subjects enrolled in China*).

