5.3.3 Efficacy Variables

Efficacy Assessments

Responses will be evaluated based on the revised guidelines by the modified International Working Group (IWG) for AML. Progressive disease is defined per European LeukemiaNet (ELN) recommendations. Subject's response is based on most recent physical examination, bone marrow results and recent hematology values. For subjects who require a delay in the next cycle of study treatment for blood count recovery after a bone marrow evaluation, hematology values up to pre-dose labs from Day 1 of the next cycle or 2 weeks from the bone marrow if there is no additional dosing can be used to determine the modified IWG response. As a significant number of the subjects in this study might have antecedent hematologic illnesses, hematologic response including transfusion independence will also be evaluated.

Criteria for evaluation are as follows:

- CR: No morphologic evidence of AML and absolute neutrophil count $\geq 10^3/\mu\text{L}$, platelets $\geq 10^5/\mu\text{L}$, red cell transfusion independence, and bone marrow with $< 5\%$ blasts, absence of circulating blasts and blasts with Auer rods; absence of extramedullary disease.
- CRi: All criteria as CR except for residual neutropenia $< 10^3/\mu\text{L}$ (1,000/ μL) or thrombocytopenia $< 10^5/\mu\text{L}$ (100,000/ μL). If all criteria for CR are met except for RBC transfusion independence, this also fulfills CRi criteria.
- PR: All of the hematologic values for a CR but with a decrease of at least 50% in the percentage of blasts to 5% to 25% in the bone marrow aspirate.

- MLFS: Less than 5% blasts in an aspirate sample with marrow spicules and with a count of at least 200 nucleated cells, absence of circulating leukemia cells, absence of extramedullary disease, and absolute neutrophils $< 10^3/\mu\text{L}$ (1,000/ μL) and thrombocytopenia $< 10^5/\mu\text{L}$ (100,000/ μL).
- RD: Failure to achieve CR, CRi, PR; in subjects surviving at least 7 days following completion of Cycle 1 treatment, with evidence of persistent leukemia by blood and/or bone marrow examination.
- MR: reappearance* of $\geq 5\%$ blasts post CR/CRi in peripheral blood or bone marrow or development of extramedullary disease.
 - * In cases with bone marrow blast percentages of 5% – 10%, a repeat marrow should be performed one week later to distinguish relapse from bone marrow regeneration.
- PD:

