 - $> 50\%$ increase in marrow blasts over baseline (a minimum 15% point increase is required in cases with $< 30\%$ blasts at baseline; or persistent marrow blast percentage of $> 70\%$ over at least 3 months; without at least a 100% improvement in ANC to an absolute level ($> 0.5 \times 10^9/\text{L}$ [500/ μL], and/or platelet count to $> 50 \times 10^9/\text{L}$ [50000/ μL] non-transfused); or
 - 50% increase in peripheral blasts ($\text{WBC} \times \% \text{ blasts}$) to $> 25 \times 10^9/\text{L}$ ($> 25000/\mu\text{L}$); or
 - New extramedullary disease

Reporting of Results

All dosed subjects will be assessed for response to treatment based on the published guidelines. Assessments will be performed at the end of Cycle 1 and every 3 cycles thereafter for response assessment. For subjects who are unblinded following the final analysis results, assessments every 3 cycles thereafter are not required. Bone marrow collection can be completed as per institutional standard of care. Subject will be assigned to one or more of the following categories by investigators:

1. complete remission;

2. complete remission with incomplete blood count recovery;
3. partial remission;
4. morphologic leukemia free state;
5. resistant disease;
6. progressive disease;
7. indeterminate (not assessable, insufficient data);
8. morphologic relapse;

MRD status if performed at investigator sites for subjects who achieve CR or CRi:

1. minimal residual disease negative;
2. minimal residual disease positive.

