8.1.4.2 Secondary Efficacy Endpoints

Fixed sequence testing procedure will be used for analyses of the secondary efficacy endpoints. If statistical test is not significant for the primary efficacy endpoint of OS, then statistical significance will not be declared for any of the secondary efficacy endpoints. Secondary efficacy endpoints are CR + CRi rate, CR + CRh rate, CR + CRi rate by the initiation of Cycle 2, CR + CRh rate by the initiation of Cycle 2, CR rate, fatigue based on the PROMIS Fatigue SF 7a, a global health status/quality of life scale (GHS/QoL) scale from the EORTC QLQ-C30, event free survival (EFS), transfusion independence rates for RBC or platelets, CR + CRi and MRD response rate, CR + CRh and MRD response rate, CR + CRi rate in biomarker subgroups (e.g., FLT3, IDH1/2), CR + CRh rate in biomarker subgroups (e.g., FLT3, IDH1/2), and OS in biomarker subgroups (e.g., FLT3, IDH1/2). To adjust for multiple testing of the key secondary efficacy endpoints, a fixed sequence testing procedure will be used. The key secondary efficacy endpoints and corresponding ranking will be specified in the statistical analysis plan (SAP).

The proportion of subjects with complete remission or complete remission with incomplete blood count recovery (CR + CRi) will be calculated based on the modified IWG criteria for AML. CR + CRi rate will be compared between treatment arms using CMH test stratified by AML status (secondary, de novo) and age ($18 - < 75, \geq 75$). In addition, 95% confidence interval will be constructed for CR + CRi.

CRh (Complete remission with partial hematologic recovery) is a derived response based on bone marrow blast and hematology lab values. A response of CRh is achieved when the following criteria are met:

- Bone marrow with $< 5\%$ blasts

- Peripheral blood neutrophil count of $> 0.5 \times 10^3/\mu\text{L}^*$
- Peripheral blood platelet count of $> 0.5 \times 10^5/\mu\text{L}^*$
- A 1 week (≥ 7 days) platelet transfusion-free period prior to the hematology lab collection

* For a bone marrow sample collected before the last cycle of study treatment, the hematology lab results collected from the date of the bone marrow sample collection up to the Day 1 of a subsequent cycle of study treatment will be used for CRh analysis.

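### The written CRh criteria do not require absence of circulating blasts or extramedullary disease, so an assessment the protocol classes as resistant disease, progression or relapse can count as a response

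*SAP*

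**What the plan says.** SAP 10.3.2 describes CRh as a "derived response based on bone marrow blast and hematology lab values. A subject achieves a CRh when meeting the following criteria". Protocol 8.1.4.2 has the same list, introduced by "A response of CRh is achieved when the following criteria are met". The four criteria are:

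- marrow blasts below 5%;
- neutrophils above 0.5 × 10³/µL;
- platelets above 0.5 × 10⁵/µL;
- at least 7 days free of platelet transfusion before the blood sample.

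Investigators do not assign CRh. It is not among their response categories in Protocol 5.3.3, and the Synopsis says the sponsor derives it alongside the investigator's IWG assessment. The written rule therefore decides who is a CRh responder. Under SAP 10.3.2 a CRh counts whenever it occurs on study.

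The other categories in Protocol 5.3.3 look beyond the marrow. MLFS requires "absence of circulating leukemia cells, absence of extramedullary disease". CR requires no circulating blasts and no extramedullary disease, and CRi inherits both conditions. Resistant disease (RD) is failure to reach CR, CRi or PR "with evidence of persistent leukemia by blood and/or bone marrow examination". Morphologic relapse (MR) is the reappearance of at least 5% "blasts post CR/CRi in peripheral blood or bone marrow or development of extramedullary disease". Progressive disease (PD) includes "New extramedullary disease" on its own, or a rise in peripheral blasts above a threshold.

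**The concern.** CRh is reported as a form of complete remission, yet on residual leukaemia outside the marrow it is looser than MLFS, which is not a response in any ranked endpoint. RD, MR and PD can each be met with marrow blasts below 5%. If blood counts are adequate, the same assessment then satisfies all four CRh criteria.

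CR + CRh is rank 2 in the US hierarchy (SAP Table 8). CRh enters ranks 2, 5, 7, 9 and 15: overall, in the IDH1/2 subgroup, by the start of Cycle 2, with MRD response, and in the FLT3 subgroup. It enters none of the 14 EU endpoints (Table 7). Where the assessment is PD or confirmed MR, one visit could be both a CRh response and an EFS event (SAP 10.3.8). It could also both start and end the duration of CR + CRh (SAP 10.4.4), giving a duration of zero.

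**Working it through.** **Definitions side by side** (Protocol 5.3.3; SAP 10.3.2)

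| Category | Marrow blasts | Circulating blasts absent? | Extramedullary disease absent? |
|---|---|---|---|
| CR | < 5% | required | required |
| CRi | < 5% | required (from CR) | required (from CR) |
| MLFS | < 5% | required | required |
| CRh | < 5% | not mentioned | not mentioned |

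**Applying the four CRh criteria to constructed assessments.** In every row the counts and transfusion-free interval meet the CRh criteria.

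| Assessment | Protocol category | CRh as written |
|---|---|---|
| Marrow 4%, circulating blasts, no prior response | RD (cannot be CR, CRi or MLFS; PR needs 5–25% marrow blasts) | yes |
| Marrow 4%, new extramedullary disease | PD | yes |
| After CRi: marrow 4%, peripheral blasts 6% | MR | yes |
| After CRi: marrow 3%, extramedullary disease | MR | yes |
| Marrow 6% | not relevant | no |

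The RD case can arise at the scheduled end-of-Cycle-1 marrow, and so feeds directly into CR + CRh by the start of Cycle 2. A marrow is also called for "Upon concern for relapse or progressive disease", which is when the MR and PD cases would be sampled.

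**Does other text close the gap?**

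- Protocol 8.1.4.2 says the CR + CRh rate follows the modified IWG criteria, but the protocol's IWG list has no CRh category from which to take the missing conditions. The SAP does not repeat the reference.
- SAP 10.1 drops response data after the cutoff, after post-treatment therapy, or after a premature unblinding. It does not drop data at PD or MR.
- No rule bars an assessment rated RD, PD or MR from being CRh.

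**Size.** Only a subject with no other valid CR or CRh changes the rate.

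- Per subject: 1/140 = 0.71 points (venetoclax); 1/70 = 1.43 points (placebo).
- Assuming 0 to 3 such subjects per arm, the rate difference is distorted by at most +3/140 = +2.1 points and at least −3/70 = −4.3 points.
- In a mutation subgroup at the 30-subject floor (Table 8, footnote b), with an assumed 20:10 split, one subject is worth 1/20 = 5 points or 1/10 = 10 points.

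**Effect on the test.** I used an unstratified one-sided Mantel-Haenszel test, z = (a − E)/√V, with E = 140m/210 and V = 140·70·m(210 − m)/(210²·209). Here a is the number of venetoclax responders and m the total number of responders. Placebo is 8/70, from the roughly 11% CR + CRi rate for LDAC in Protocol 3.2. The 78% is the CR + CRi rate for the combination in Protocol 3.0, and both are proxies for CR + CRh. The 50% and 35% rates are assumptions.

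| Venetoclax responders | p | p with 3 removed |
|---|---|---|
| 109/140 (78%) | 4.0 × 10⁻²⁰ | 7.2 × 10⁻¹⁹ |
| 70/140 (50%) | 2.7 × 10⁻⁸ | 1.1 × 10⁻⁷ |
| 49/140 (35%) | 0.00015 | 0.00042 |

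For the last row, m = 57, E = 38 and V = 9.27, so z = 11/3.045 = 3.61. With 3 removed, m = 54, E = 36 and V = 8.96, so z = 10/2.993 = 3.34. None of these crosses one-sided 0.025. The planned test is stratified and its boundary comes from alpha spending, so the p-values are illustrative.

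**The case against.** The omission itself is not disputed. The case against concerns its reach.

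- **The routes are unequal.** An MR after a CR, or after a CRi that already met CRh, cannot change the rate because the subject already counts. PD through peripheral blasts needs more than 25 × 10⁹/L together with a marrow below 5% and adequate counts, which nothing in the documents suggests will occur. RD is the main practical route, and there the label depends on the investigator's judgement; an indeterminate category also exists.
- **The downstream effects miss the main route.** RD at the end of Cycle 1 is not an EFS event, because SAP 10.3.8 requires at least 6 cycles for treatment failure. RD does not end duration of CR + CRh, which is an exploratory endpoint.
- **Exposure is limited.** Protocol 5.1.4 states "For subjects who had RD, MR or PD at time of study drug discontinuation, survival phone calls will be conducted every 2 months", so few qualifying assessments would follow discontinuation. Rank 9 also needs an MRD response, and subgroups under 30 drop below EFS in the ranking.
- **There is partial cover.** CR + CRi (US rank 3) carries the full conditions, and SAP 10.1 promises IRC-based sensitivity analyses in general.
- **The size range has no documentary anchor.** Each extreme puts all three assumed cases in one arm of a blinded trial.

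All of this narrows the consequences, and the size range is indeed arithmetic on an assumption, not an estimate of bias. None of it removes the defect. The rule as written gives the wrong answer for these assessments, and the specific IRC lists (Protocol 8.1.5, SAP 10.5) leave out CR + CRh.

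**Conclusion.** The concern holds. The four criteria are presented as sufficient, they lack two conditions that CR, CRi and MLFS all carry, and no other text supplies them. The finding concerns the written rule only, since the documents do not show how CRh was programmed.

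The likely effect is small: 0.7 or 1.4 points per affected subject, and between −4.3 and +2.1 points on the rate difference if 0 to 3 subjects per arm are assumed. No whole-trial scenario examined changes a conclusion. A result near its boundary could change, most plausibly in a small mutation subgroup. The EFS and zero-duration overlaps are confined to assessments that are PD or relapse. It should be corrected because it bears on the validity and reported size of the first US endpoint after OS, and correction is cheap.

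**What to change.** Add to the criteria in SAP 10.3.2 and Protocol 8.1.4.2: no circulating blasts in the hematology sample used for CRh, and no extramedullary disease at the corresponding disease assessment. Treat an unreported blast count as none detected, because Protocol Table 4 collects it only when blasts are found.

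Protocol 1.1 states that the final efficacy analysis has been performed, so the order of work is:

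1. Confirm whether the programmed derivation already applied these conditions. If it did, only the text needs correcting.
2. If it did not, report CR + CRh with the conditions as a labelled post hoc sensitivity analysis. It does not replace the ranked test.
3. List the subjects whose only qualifying CRh assessment had circulating blasts, extramedullary disease, or a concurrent RD, PD or MR rating. The rating check matters because SAP 10.3.2 allows a window of blood samples, and a blast-free sample could be used while another in the window shows blasts.

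The cost is one line in each document. The blast count is already a laboratory field. The documents describe no separate field for extramedullary disease, so it may have to be read from disease assessment and physical examination records for the few flagged subjects. The CR + CRh rate can only stay the same or fall.

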10.3.4 Complete Remission (CR) Rate

CR rate will be defined as the proportion of subjects who achieved a complete remission (CR) at any time point during the study per the modified IWG criteria for AML. Subjects

who are randomized but have no IWG disease assessment will be considered to be non-responders in the calculation of CR rate. All subjects in the full analysis set will be included in the analysis.

CR rate will be compared between treatment arms using Cochran-Mantel-Haenszel (CMH) test, stratified by AML status (de novo, secondary) and age ($18 - < 75, \geq 75$). In addition, the 95% confidence interval for CR rate based on the binomial distribution (Clopper-Pearson exact method) by treatment arms will be provided. The risk difference and 95% confidence interval for the risk difference (exact unconditional confidence limits) will also be provided.

